5.2.3 Hypotheses

The long-term safety of oral edaravone will be evaluated.

6 STUDY DESIGN

6.1 Overall Study Design

This is a Phase 3, multi-center, open-label safety extension study. The study will evaluate the long-term safety of oral edaravone at a dose of 105 mg administered once daily for 10 days out of 14, followed by a 14-day drug-free period. This study will be continued until the earlier date when oral edaravone is commercially available at each site in Japan or August 2023.

Eligible subjects who will complete Week 96 of MT-1186-A03 study or Week 48 of MT-1186-A04 study will be enrolled in this study (Study MT-1186-A-301). The subjects must continue to fast at least 1 to 2 hours post-dose before the next meal (eg, breakfast). The cycle of doses consists of 28 days, or a dose of 105 mg administered once daily for 10 days out of a 14-day period, followed by a 14-day drug-free period.

Subjects who discontinue from the study will complete the procedures listed in ET (refer to Table 1 for further information) within 7 days of discontinuation.

Further details can be found in the Study Schema (Figure 1).

This study will be continued as a post marketing study since the date of approval by the regulatory authority in Japan in order to provide the subjects with the opportunity of taking oral edaravone.

6.2 Rationale for Study Design

The rationale for the study design is to confirm the long-term safety and tolerability of oral edaravone at a 105 mg dose and provide the subjects with the opportunity of taking oral edaravone.

6.2.1 Risk/Benefit Assessment

Edaravone has been evaluated in ten Phase 1 studies in healthy subjects in Japan and Europe and has been evaluated in other clinical studies, including ALS, as follow.

- 8 clinical studies in acute ischemic stroke (AIS) subjects in Japan and Europe
- 3 clinical studies in subarachnoid hemorrhage subjects in Japan
- 5 clinical studies in ALS in Japan
- 7 oral clinical Phase 1 studies in healthy volunteer or ALS in Japan

The treatment of AIS and ALS in Japan states that IV edaravone (MCI-186) edaravone (MCI-186) is contraindicated in subjects with severe renal impairment and should be administered with care in subjects with hepatic impairment. Conversely, there are no contraindications or warnings to subjects with renal or hepatic impairment in the United States Package Insert (USPI) for treatment of ALS in the US.

In the USPI (IV edaravone) Warnings and Precautions Section, hypersensitivity reactions (redness, wheals, and erythema multiforme) and cases of anaphylaxis (urticarial, decreased blood pressure, and dyspnea) have been reported in spontaneous postmarketing reports with edaravone. Edaravone contains sodium bisulfite, a sulfite that may cause allergic type reactions, including anaphylactic symptoms and life-threatening or less severe asthmatic episodes in susceptible people. The overall prevalence of sulfite sensitivity in the general population is unknown. Sulfite sensitivity occurs more frequently in asthmatic people.

In the USPI (IV edaravone) adverse reactions section, the most common adverse reactions observed during clinical studies were contusion, gait disturbance, headache, dermatitis, eczema, respiratory failure, respiratory disorder, hypoxia, glycosuria, and tinea infection.

Risk related to Covid-19 was also assessed. Edaravone is not known to alter immune function. However, there may be additional risk to participants due to exposure to Covid-19 during study related visits (dependent on the country/region conditions). Subjects will be encouraged to observe social distancing, wear face masks/coverings and avoid social gatherings during the conduct of the clinical trial and site visits, as long as COVID-19 is prevalent. Additionally, the Sponsor will monitor country conditions and prepare contingency plans for Covid-19 related restrictions that may prevent site visits.

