This randomized, open-label, crossover, single dose clinical pharmacology study was conducted in 36 healthy volunteers to assess the comparative bioavailability of oral edaravone when administered via nasogastric tube (a surrogate for PEG/RIG administration) compared to oral administration. Preliminary PK data obtained from 36 subjects showed that both C_{max} and AUC fell within equivalence criteria. These data indicate that oral edaravone can be administered orally and via PEG/RIG without any need for dose adjustment.

Study MT-1186-A01

This study evaluated the safety of oral edaravone for a period of 48 weeks in patients with ALS. One hundred eighty five subjects were enrolled and 139 subjects in enrolled population were completed the 48-week study period. A total of 961 TEAEs were experienced by 175 (94.6%) subjects. Of these, TEAEs related to study treatment were reported by 46 (24.9%) subjects, serious TEAEs were reported by 48 (25.9%) subjects. The most frequently reported TEAEs by PT were fall (22.2%), muscular weakness (21.1%), and constipation (17.8%). The most frequently reported TEAEs related to study drug by PT were fatigue (3.2%), dizziness (2.7%), headache (2.2%), and constipation (2.2%). Twelve subjects died during the study period: 4 subjects died from respiratory failure, 2 subjects died from pneumonia, and 2 subjects died from ALS. The following causes of death were reported for 1 (0.5%) subject each: diabetic ketoacidosis and acute respiratory failure, feeding disorder, completed suicide, and lung disorder.

In order to evaluate the long-term safety of oral edaravone, Study MT-1186 A03 is ongoing as an extension study of Study MT-1186 A01. In addition, Study MT-1186-A02 and its extension study MT-1186-A04 are ongoing for the purpose of comparing the efficacy and safety of the following two dosing regimens of oral edaravone.

- Oral edaravone 105 mg administered once daily (regimen denoted as daily) in Cycles 1 through 12
- Oral edaravone 105 mg administered for 14 days, followed by placebo for 14 days in Cycle 1, and subsequently, repeat oral edaravone 105 mg administered for 10 days followed by placebo for 18 days (regimen denoted as on/off) in Cycles 2 through 12

Oral edaravone was approved by the US FDA (Radicava ORS ®) in 2022 as a new treatment option to delay disease progression in ALS patients.

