6.2.2 Rational for Dose Selection

Findings from Study MT-1186-J03 demonstrated that a 105 mg oral suspension dose of edaravone has an equivalent AUC to the approved 60 mg/60 min IV dose (geometric mean ratio [90% CI]: 0.977 [0.917, 1.041]). The geometric mean ratio of the C_{max} of the 105 mg oral suspension compared to the 60 mg/60 min IV infusion was also within bioequivalence range, but the upper limit of 90% CI exceeded 1.25 (geometric mean ratio [90% CI]: 1.217 [1.090, 1.359]). This was the dose given in the MT-1186-A01 study, and therefore, the 105 mg dose has been selected for this study as well.

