7 SELECTION AND WITHDRAWAL OF SUBJECTS

7.1 Number of Subjects

Approximately 30 subjects who have successfully completed Study MT-1186-A03 or Study MT-1186-A04 will potentially be enrolled. The total number of subjects to be enrolled will depend on the number of subjects who complete Week 96 of Study MT-1186 A03 or Week 48 of Study MT-1186 A04 and are eligible and consented to participate in this extension study.

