7.3 Inclusion Criteria

Subjects who meet all the following criteria will be considered eligible to participate in the study:

1. Subjects must provide a signed and dated informed consent form (ICF) to participate in the study.
2. Subjects must be able (in the judgment of the Investigator) to understand the nature of the study and all risks involved with participation in the study.
3. Subjects must be willing to cooperate and comply with all protocol restrictions and requirements.
4. Subjects who successfully complete Week 96 of Study MT-1186-A03 or Week 48 of Study MT-1186-A04 and have been compliant with study drug (80-120%).

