12.6 Dose Adjustment Criteria

Dose adjustments of oral edaravone will not be allowed.

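### The protocol cites a Japanese contraindication of IV edaravone in severe renal impairment, but no entry or withdrawal criterion of this Japanese extension names renal function (low severity, cheap to fix)

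*Protocol*

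**What the plan says.** Protocol 6.2.1 reports that, in the Japanese treatment of stroke and ALS, IV edaravone "is contraindicated in subjects with severe renal impairment" and calls for care in hepatic impairment. It then says that "there are no contraindications or warnings to subjects with renal or hepatic impairment in the United States Package Insert". It does not say which position this study takes.

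The study runs "until the earlier date when oral edaravone is commercially available at each site in Japan or August 2023" (6.1). The dose rests on the finding that a "105 mg oral suspension dose of edaravone has an equivalent AUC to the approved 60 mg/60 min IV dose" (6.2.2). Section 12.6 adds: "Dose adjustments of oral edaravone will not be allowed".

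Entry is by roll-over: "Approximately 30 subjects who have successfully completed Study MT-1186-A03 or Study MT-1186-A04 will potentially be enrolled" (7.1). Section 7.3 has four inclusion items and 7.4 has four exclusion items. The third exclusion leaves suitability to the investigator. Under 7.2 and 8.1.1, eligibility is checked against the results of the final parent-study visit (Week 96 of A03 or Week 48 of A04). Section 7.6 lists nine withdrawal items, one of which gives numerical ALT, AST and bilirubin limits.

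Serum creatinine and BUN are in the chemistry panel (10.6.2). Section 13.5 leaves the clinical significance of an abnormal result to the investigator.

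**The concern.** The protocol identifies a class of patient who, under the IV labelling of the study country, should not receive this active substance. It then writes criteria that never mention that class. With a fixed dose, the only protection is not to start or to stop, and the text gives no renal prompt for either decision.

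Two sites looking at the same creatinine could reasonably decide differently, and both would comply with the protocol. At stake is who may be dosed in a study whose primary objective is safety. No estimate is at stake: the analyses are descriptive and the sample size is not power-based (15.1, 15.3.1).

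**Working it through.** There is no figure in the plan to reproduce. The check is a count of criteria and a comparison of sections.

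**1. Criteria naming renal function**
- Inclusion (7.3): consent, understanding, cooperation, parent-study completion with compliance. Count: 0 of 4.
- Exclusion (7.4): pregnancy and contraception, suicide risk, investigator judgement, no oral or PEG/RIG route. Count: 0 of 4.
- Withdrawal (7.6, top-level items): subject request, found ineligible, AEs, pregnancy, tracheostomy, permanent ventilation, disease exacerbation, liver dysfunction, noncompliance. Count: 0 of 9.
- Total: 0 of 4 + 4 + 9 = 17. The synopsis lists of inclusion and exclusion criteria agree.

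**2. Does the IV statement bear on the oral dose?**
- The oral/IV AUC ratio is 0.977 with 90% CI 0.917 to 1.041 (6.2.2). Average exposure on the oral dose is therefore between 1 − 0.917 = 8.3% lower and 1.041 − 1 = 4.1% higher than on IV.
- The Cmax ratio is 1.217 (1.090 to 1.359).
- Section 4.2 (Study J03) gives sulfate and glucuronide conjugate AUCs of 1.3 and 1.7 times those after IV.
- None of these gives a reason to set the IV warning aside on grounds of lower exposure. They come from healthy volunteers, so they say nothing direct about patients with renal impairment.

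**3. Liver and kidney compared**
- Hepatic impairment: the cited Japanese position is caution. Section 7.6 has four explicit stopping conditions.
- Severe renal impairment: the cited Japanese position is contraindication. Section 7.6 has none.
- The protocol is therefore willing to write organ-specific rules in this extension, and the condition with the stronger cited warning has no rule.

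**4. What does stand between such a subject and the drug**
- At entry: exclusion 3. The Day 1 chemistry is the final parent-visit chemistry (Table 1), so a current creatinine and BUN are available.
- After entry: withdrawal for an AE that makes continuation difficult, or because the subject is found ineligible (7.6). Sections 13.5 and 8.1.3 supply the judgement on laboratory results and the option of an unscheduled safety visit.
- All of these are general. None carries a renal definition or cut-off.

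**5. Where a named rule would act**
- Table 1 schedules chemistry at Day 1 (the parent visit), Week 24 and EOS/ET.
- SAP 7.2 records that no subject reached Week 24. As conducted, the only scheduled chemistry after entry was at EOS/ET, so an entry criterion carries most of the value.

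**The case against.** The strongest reply is that exclusion 3 is a working safeguard. The investigator has the warning in 6.2.1, a creatinine and BUN from the same visit, and authority to refuse entry. Later, 7.6 allows withdrawal on two general grounds. Subjects have also completed A03 or A04 on study drug with 80 to 120% compliance. The parent protocols, the Investigator's Brochure or the package insert (13.10) may already deal with renal function. The contraindication is reported for the IV product, and the US label has none. Finally, the proposed line still needs clinical judgement and a cut-off that the documents do not give.

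Most of this stands, and it limits the point. Three stronger readings are tempting, and the documents support none of them:
- **That nothing bars such a subject.** Exclusion 3 is itself a criterion, and a subject with known severe impairment need not pass it.
- **That renally impaired subjects were dosed, or that the parent studies did not screen for the condition.** The documents contain neither the renal results nor the parent criteria.
- **That oral edaravone is contraindicated in Japan in this group.** The protocol reports this for IV only.

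The objection does not remove the gap in the text. The Brochure and package insert are named as reference safety information, not as entry or stopping rules. Tolerating earlier dosing does not establish adequate renal function at roll-over. A definition taken from the label or Brochure would not make decisions uniform, but it would put the same question to every site.

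**Conclusion.** The point holds as a cheap improvement of low severity. Renal function is named in 0 of 17 criteria, although the protocol itself cites a contraindication for the study country and sets liver rules on a weaker warning. As written, a subject in that class can be enrolled and kept on drug at the investigator's discretion.

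The number affected among the approximately 30 roll-over subjects is unknown and may be zero. The conclusion concerns this protocol's own criteria. It assumes that the IV statement is relevant to an oral dose chosen to match IV exposure. It would lose practical weight if the parent protocols, Brochure or package insert already impose a renal rule on these subjects. No estimate or endpoint analysis changes.

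**What to change.** Add severe renal impairment to the exclusions in 7.4 and to the matching synopsis list. Take the definition from the Japanese label or the Investigator's Brochure, and judge it at Day 1 from the parent-visit creatinine and BUN together with clinical history. Add the same condition to 7.6 for any later scheduled or unscheduled chemistry.

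Keep exclusion 3. Section 4.1 describes muscle atrophy as a dominant feature of ALS, and loss of muscle can lower creatinine, so a laboratory cut-off alone could understate the impairment.

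The cost is one line in each section and no new test. The downside is that a roll-over subject who tolerates the drug could become ineligible. If the sponsor prefers no criterion, one sentence in 6.2.1 saying why the cited contraindication does not apply here would at least close the gap in the reasoning.

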6.2.2 Rational for Dose Selection

Findings from Study MT-1186-J03 demonstrated that a 105 mg oral suspension dose of edaravone has an equivalent AUC to the approved 60 mg/60 min IV dose (geometric mean ratio [90% CI]: 0.977 [0.917, 1.041]). The geometric mean ratio of the C_{max} of the 105 mg oral suspension compared to the 60 mg/60 min IV infusion was also within bioequivalence range, but the upper limit of 90% CI exceeded 1.25 (geometric mean ratio [90% CI]: 1.217 [1.090, 1.359]). This was the dose given in the MT-1186-A01 study, and therefore, the 105 mg dose has been selected for this study as well.

7 SELECTION AND WITHDRAWAL OF SUBJECTS

7.1 Number of Subjects

Approximately 30 subjects who have successfully completed Study MT-1186-A03 or Study MT-1186-A04 will potentially be enrolled. The total number of subjects to be enrolled will depend on the number of subjects who complete Week 96 of Study MT-1186 A03 or Week 48 of Study MT-1186 A04 and are eligible and consented to participate in this extension study.

7.2 Recruitment Methods

Subjects will be recruited via completion of the Study MT-1186-A03 or Study MT-1186-A04. Only subjects who are eligible for the study based upon their Week 96 procedures from the Study MT-1186-A03 or Week 48 procedures from the MT-1186-A04 will be enrolled.

7.3 Inclusion Criteria

Subjects who meet all the following criteria will be considered eligible to participate in the study:

1. Subjects must provide a signed and dated informed consent form (ICF) to participate in the study.
2. Subjects must be able (in the judgment of the Investigator) to understand the nature of the study and all risks involved with participation in the study.
3. Subjects must be willing to cooperate and comply with all protocol restrictions and requirements.
4. Subjects who successfully complete Week 96 of Study MT-1186-A03 or Week 48 of Study MT-1186-A04 and have been compliant with study drug (80-120%).

7.4 Exclusion criteria

Subjects who meet any of the following criteria will be excluded from the study:

1. Subjects of childbearing potential who are not tested negative by a pregnancy test, subjects who are breastfeeding, and subjects who are unwilling to use a highly effective method of contraception from the Visit #1 until 3 months after the last dose of study medication. Refer to Attachment 2 for additional contraceptive information.
2. Subjects who have a significant risk of suicide. Subjects with any suicidal behavior or suicidal ideation of type 4 (active suicidal ideation with some intent to act, without a specific plan) or type 5 (active suicidal ideation with

specific plan and intent) based on the C-SSRS at Week 96 of the A03 study or at Week 48 of the A04 study.

3. Subjects who are not eligible to continue in the study, as judged by the Investigator.
4. Subjects who cannot receive drugs orally or via PEG/RIG.

7.5 Screen Failures

If a subject has not met all eligibility criteria at the beginning of the treatment period, the subject will be registered as a screen fail and cannot be enrolled into the study.

7.6 Withdrawal of Individual Subjects

A subject will be withdrawn from the study if the subject meets any of the following criteria:

- Requests to be withdrawn from the study;
- Has been found to be ineligible for participation in the study;
- The investigator (or subinvestigator) concludes that a subject should be withdrawn if continuation in the study is difficult due to AEs (e.g., hypersensitivity reactions);
- Is pregnant;
- Requires tracheostomy;
- Requires permanent assisted mechanical ventilation (≥ 23 hours/day);
- The investigator (or subinvestigator) judges' continuation of the study to be inappropriate due to exacerbation of the primary disease;
- Development of significant liver dysfunction:
 - ALT or AST greater than 8 times the ULN;
 - Persistent ALT or AST of greater than 5 times the ULN for at least 2 weeks;
 - ALT or AST greater than 3 times the ULN AND elevated total bilirubin greater than 2 times ULN;
 - Symptoms consistent with liver dysfunction (e.g., fatigue, nausea, vomiting, abdominal pain/tenderness, fever, rash, eosinophilia $>5\%$) with concomitant ALT or AST greater than 3 times the ULN.

Note: Subjects meeting these criteria do not require withdrawal if alternative etiology is identified on discussion with the Sponsor.

- Noncompliance (i.e., misses more than 20% of doses in 2 consecutive dosing cycles, after consultation with the Sponsor).

If a subject is withdrawn prematurely from the study, the date the subject is withdrawn from the study and the reason for withdrawal will be recorded in the electronic case report form (eCRF).

In the event that a subject drops out of the study at any time, the reason for discontinuation must be fully documented in the source documents and the eCRF. The Investigator site personnel will document the AEs and any other assessments in the source documents and will make every effort to complete all required early termination (ET) assessments. Study sites must make all efforts to follow-up.

Subjects who are withdrawn from the study following enrollment may not re-enter the study.

The study may be terminated by the Sponsor at any time upon becoming aware of data that could compromise the safety and/or well-being of subjects or for any other reason it deems appropriate.

8 STUDY PLAN

8.1 Description of Study Periods

Refer to Table 1 for an outline of procedures required at each study period and/or visit.

Prior to performing any study procedures, the Investigator (or designated personnel) will ensure that the subject is given full and adequate oral and written information about the study and the subject must sign the ICF, as described in Section 16.2.1.

8.1.1 Open-label Treatment Period

Subjects who successfully completed the Week 96 study procedures from Study MT-1186-A03 or Week 48 study procedures from Study MT-1186-A04 will remain at the study clinic and inclusion and exclusion criteria will be reviewed against those results to confirm eligibility. Eligible subjects will then be enrolled, and dosing will begin on Day 1 (Visit 1).

Study visits will occur onsite, in the patient home, or via a telephone call per the Schedule of Assessments (Table 1). The investigator (or designee) should instruct the subject to contact the study site if any unusual circumstances (eg, adverse events) occur outside of the clinic visits.

8.1.2 End of Treatment/Early Termination (EOS/ET)

The assessment at Visit 3, EOS will be conducted for subjects who complete the open-label treatment period (earlier date when oral edaravone is commercially available at each site in Japan or August 2023), per the Schedule of Assessments (Table 1). If it becomes possible to prescribe commercially available oral edaravone at each site, subjects will be asked to visit the study site immediately at the end of the last cycle to evaluate EOS.

For subjects who terminate early from the study, assessments should be performed per the Schedule of Assessments (Table 1) within 7 days of study discontinuation.

Any unresolved AE or SAE will be followed up according to Section 13.8.

In the event that a subject elects not to return to the clinical site for the ET Visit, the Investigator must make every effort to contact the subject to review all AEs. In the event that a subject drops out of the study at any time, the reason for discontinuation must be fully documented in the source documents and the eCRF. The Investigator site personnel will document the AEs and any other assessments in the source documents and will make every effort to complete all required ET assessments.

8.1.3 Unscheduled Visits

An unscheduled visit is defined as any visit to the Investigator site outside of the protocol specified time points due to safety reasons or when a repeated measurement is required (e.g., obvious measurement errors, measuring device failure, confirmation of out-of-range results), where the subject is seen by study personnel.

